# **Statistical Methodology**

#### **Data Summary**

All data entry and analysis will be done by the Mayo Clinic Division of Biostatistics.

The following is a detailed proposal of statistical analyses planned for data collected during the study. In general, data will be summarized by treatment group and nominal study visit, where applicable.

For parameters represented by continuous variables (e.g., ROM), the summaries will consist of the mean, median, standard deviation, minimum, and maximum values. Both the actual values at each nominal visit and the improvement from baseline at each post-baseline visit for each treatment group and their difference will be presented with its 95% confidence intervals. The improvement from baseline will also present the corresponding paired t-test p-values.

For categorical variables (e.g., subsidence), the number of events, person-years of follow-up, and the corresponding event rates with 95% confidence intervals will be presented.

In addition, the rate ratios (relative risk) of the treatment groups along with 95% confidence intervals will be presented.

Descriptive statistics and statistical comparisons for important demographic, efficacy, and safety variables will be provided in tables. All data collected on the case report forms will be provided in data listings, which will be sorted by treatment group and patient number.

Documentation of statistical analyses will be provided in a statistical appendix. All statistical analyses will be completed using SAS®, version 9 or higher (SAS Institute Inc,

Cary, NC), and Splus, version 7 or higher (Insightful Corporation, Seattle, WA).

All statistical tests will be two-sided and p-values less than 0.05 will be considered

significant.

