**Sample Size Justification** 

Revision rates for total knee arthroplasty are approximately 0.5% per year over the life of

the knee. At ten years, this rate would be expected to be 5%. Within the Triathlon PS,

X3 has been shown to reduce wear over N2Vac by up to 68%. Therefore, by assuming

all revisions could be attributed to polyethylene debris the X3 can be assumed to have a

revision rate of 1.6% at 10 years. Assuming that the X3 knees have a 10-year revision

rate of 1.6% and that the corresponding rate in the N2Vac knees is 5.0% yields a rate

ratio of 0.32 (or 3.1 for N2Vac/X3). In order to have 80% power to detect this rate ratio

as being significantly different from 1.00 will require that 26 events (revisions) are

observed during the 10-year follow-up period. Assuming the overall 10-year revision rate

is 5%, the sample size required to observe 26 revisions is 26/0.05=520, or n=260 in each

treatment group. By factoring in a 10% lost to follow-up rate within the ten-year period,

the total enrollment of about 572 subjects (286 in each group) will be needed.

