# **Efficacy Analyses**

#### Methods

Primary Parameter: The relative risk of revision (X3 relative to N2Vac) at ten years will be computed and a 95% confidence interval on the rate ratio computed, assuming a Poisson distribution. If the upper end of the confidence interval for the rate ratio is less than 1.0, then the superiority hypothesis will be supported. Otherwise, if the upper end of the confidence interval is less than 1.2, then the non-inferiority hypothesis will be supported. Secondary Parameters: The categorical secondary efficacy parameters will be analyzed at each nominal visit by computing the 95% confidence interval for the rate ratio (relative risk) of the groups as above. The clinically significant difference ( $\Delta_0$ ) is as presented on page 13 above. The continuous secondary efficacy parameters will be analyzed at each nominal visit. The 95% confidence interval on the difference between the two groups will be computed using the means, t-distribution and appropriate standard deviation. The change from baseline will also be presented and their 95% confidence interval and p-value for the paired t-test using the baseline will be presented for each nominal visit and treatment group, along with the descriptive statistics.

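### The sample size divides 26 revisions by the N2Vac rate of 5% instead of the pooled 3.3%, so about 17 revisions are expected and superiority power is about 50–65%, not 80%

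*Combined protocol and SAP*

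**What the plan says.** Sample Size Justification starts from a general knee-replacement revision rate of 0.5% per year, hence 5% at ten years. It derives 1.6% for X3 from a 68% reduction in wear. It then takes a "rate of 1.6% and that the corresponding rate in the N2Vac knees is 5.0% yields a rate" ratio, given as a "ratio of 0.32 (or 3.1 for N2Vac/X3). In order to have 80% power to detect this rate ratio". Detecting that ratio "as being significantly different from 1.00 will require that 26 events (revisions) are" observed over ten years.

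The next sentence converts events to patients. It supposes an overall ten-year revision rate that "is 5%, the sample size required to observe 26 revisions is 26/0.05=520, or n=260 in each" group. A 10% allowance for loss raises 520 to 572.

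The decision rule is in the Methods part of Efficacy Analyses. The relative risk gets "a 95% confidence interval on the rate ratio computed, assuming a Poisson distribution", and "If the upper end of the confidence interval for the rate ratio is less than 1.0, then the superiority hypothesis will be supported". Data Summary adds: "All statistical tests will be two-sided and p-values less than 0.05 will be considered" significant.

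**The concern.** The event target and the conversion to patients rest on different assumptions. The 26 events belong to arm rates of 5.0% and 1.6%. The divisor should be the revision rate averaged over both arms under those same rates. The plan uses 5%, which it has just assigned to the N2Vac arm. Nothing else in the document supports 5% as a rate over both arms combined.

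This is the only power statement for the primary endpoint. If it is too high, a ten-year result that misses superiority could be read as evidence against a benefit of X3, when the design had close to even odds of missing the benefit it assumed. No interim analysis is planned.

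**Working it through.** **Inputs** (Sample Size Justification unless noted): N2Vac 5.0%; X3 1.6%; ratio 0.32; 26 events; 80% power; 1:1 allocation; 10% loss; 286 enrolled per group. Two-sided 0.05 is from Data Summary. The rule that the upper 95% limit must lie below 1.0 is from Efficacy Analyses, Methods.

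**1. The plan's own figures.** Usual events formula for equal groups: 4 × (1.96 + 0.842)² / ln(0.32)² = 24.2 events. This is close to 26, and the same formula gives 83% power at 26. Then 26/0.05 = 520, and 520 × 1.10 = 572. The figures reproduce, but only with 5% as the pooled rate.

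**2. The pooled rate.** (5.0% + 1.6%)/2 = 3.3%. For a pooled 5% to hold with a ratio of 0.32, N2Vac would need 2 × 5%/1.32 = 7.6% and X3 0.32 × 7.6% = 2.4%. The paragraph states neither.

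**3. Expected revisions at the stated rates.**
- 260 per group: 260 × 0.05 + 260 × 0.016 = 13.0 + 4.2 = 17.2.
- 286 × 0.90 = 257.4 per group: 257.4 × 0.066 = 17.0.
- All 286 per group followed for ten years: 286 × 0.066 = 18.9.

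The Poisson probability of 26 or more revisions is 2.8%, 2.5% and 6.9% respectively.

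**4. Superiority power.** The interval columns sum the probabilities of independent Poisson counts in the two arms over all outcomes whose upper 95% limit is below 1.0. The Wald range depends on whether a zero count is treated as a non-success or has 0.5 added. The last column is Φ(√events × |ln 0.32|/2 − 1.96).

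| Follow-up per group | Expected events | Exact | Wald | Score | Events formula |
|---|---|---|---|---|---|
| 257.4 (lost patients contribute nothing) | 17.0 | 49% | 52–54% | 58% | 65% |
| 271.7 (assumption: 10% loss spread evenly, 286 × 0.95) | 17.9 | 52% | 55–57% | 61% | 67% |
| 286 (no loss) | 18.9 | 54% | 59–60% | 64% | 70% |
| 394 (26 events at 3.3%) | 26.0 | 70% | 75–76% | 78% | 83% |

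**5. Effect of the divisor alone.** Comparing the first and last rows within each column: 70% to 49%, 75–76% to 52–54%, 78% to 58%, 83% to 65%. The loss is 18 to 23 percentage points.

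**6. The non-inferiority rule at the same rates.** At 257.4 per group the upper limit falls below 1.2 in 64% (exact), 67–69% (Wald) or 72% (score) of trials.

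**7. Patients needed to expect 26 events.** 26/0.033 = 788 evaluable, and 788 × 1.10 = 867 enrolled with the plan's own inflation (788/0.90 = 876 if 10% of those enrolled are lost).

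**The case against.** The arithmetic is hard to contest; the objections that carry weight concern attribution and consequence.

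- **Not all of the fall from 80% to about 50% comes from the divisor.** Even with 26 expected events, an exact interval gives only 70% and a Wald interval 75–76%. This stands, so the like-for-like loss in step 5 is the figure to attribute to the division. It does not rescue 80%, because the most favourable method also falls, to 65%.
- **Counting only 257 per group may be too harsh.** Data Summary promises "the number of events, person-years of follow-up, and the corresponding event rates with 95% confidence intervals will be presented", so patients lost later would still contribute time. This stands as well. It moves exact power from 49% to 52% under even loss, and to 54% with no loss. Across all methods and follow-up cases the range is 49–70%.
- **A miss on superiority may still meet the non-inferiority rule.** True in part: the upper limit is below 1.2 in roughly 64–72% of trials. But the plan's 80% is stated against a ratio of 1.00, so it is a superiority claim.
- **The validity of the analysis is untouched.** Correct. The interval and its type I error do not depend on the sample-size paragraph, and the documents do not show whether enrolment can still change. That favours correcting the text over adding patients.

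It could also be said that 5% is a cautious overall assumption. It is the reverse: a higher pooled rate implies more events and a smaller trial.

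**Conclusion.** The concern holds and must be fixed. At the plan's own rates the design expects 17 to 19 revisions against the 26 it requires. Superiority power is about 50–65% with 257–260 per group, and at most 70% with complete follow-up under the most favourable formula. If X3 performs exactly as assumed, superiority is missed in roughly 35–50% of trials, not 20%. Part of that gap reflects the interval method, which the plan does not name; the division error by itself accounts for 18 to 23 points.

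The figures take the stated 5.0% and 1.6%, 1:1 allocation, two-sided 5% and Poisson counts as given. The even-loss case is an assumption, since the plan does not say when losses occur.

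**What to change.** Keep 572 and correct the text.

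1. In Sample Size Justification, replace the overall rate of 5% and the division giving 520 with an overall expected rate of 3.3% (5.0% and 1.6%, equal allocation). State about 17 expected revisions after 10% loss, and about 19 with complete follow-up.
2. In Efficacy Analyses, Methods, name the Poisson interval method and say whether lost patients contribute person-years.
3. Replace 80% with the power for that choice. At 257 per group this is about 49% (exact), 52–54% (Wald) or 58% (score). If person-years are used and loss is even, it is about 52%, 55–57% or 61%.

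The cost is one rewritten paragraph, a short addition to Methods and a less favourable stated power; no patients are added.

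If the team prefers to keep 26 expected events, the paragraph should give about 788 evaluable patients, or about 867 enrolled with the plan's own factor: 867 − 572 = 295 more. It should also say that this restores the event target but not 80% power under the interval rule, where power would be 70% (exact) to 78% (score). Reaching 80% would take about 438 evaluable per group with a Wald interval and about 490 with an exact one.

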**Interim Analyses and early Stopping Considerations** 

No interim analysis is planned.

# **Efficacy Analyses**

#### Methods

Primary Parameter: The relative risk of revision (X3 relative to N2Vac) at ten years will be computed and a 95% confidence interval on the rate ratio computed, assuming a Poisson distribution. If the upper end of the confidence interval for the rate ratio is less than 1.0, then the superiority hypothesis will be supported. Otherwise, if the upper end of the confidence interval is less than 1.2, then the non-inferiority hypothesis will be supported. Secondary Parameters: The categorical secondary efficacy parameters will be analyzed at each nominal visit by computing the 95% confidence interval for the rate ratio (relative risk) of the groups as above. The clinically significant difference ( $\Delta_0$ ) is as presented on page 13 above. The continuous secondary efficacy parameters will be analyzed at each nominal visit. The 95% confidence interval on the difference between the two groups will be computed using the means, t-distribution and appropriate standard deviation. The change from baseline will also be presented and their 95% confidence interval and p-value for the paired t-test using the baseline will be presented for each nominal visit and treatment group, along with the descriptive statistics.

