### **SUMMARY**

A prospective, randomized, single-blinded clinical trial is proposed to compare Stryker Orthopaedics N2Vac Polyethylene to their X3 Polyethylene when used with the Triathlon Posterior Stabilized (PS) total knee system. This is a fixed-bearing knee intended for use in patients undergoing cemented total knee arthroplasty. The devices to be used are both FDA approved via 510k clearance.

A total of 572 cases (286 per group) will be entered. Each patient will be assessed preoperatively and post-operatively at three months and two, five, seven and ten years. The primary endpoint will be the revision rate at ten years. This outcome will be evaluated using event rates analysis assuming a Poisson distribution. Additional endpoints, including the instance of mortality, revision surgery, deep vein thrombosis, pulmonary embolus, neurovascular complication, and infection will be evaluated in the same manner. Other outcome measures incorporated in the Knee Society Clinical rating scale will undergo appropriate generalized linear regression for the type of outcome involved.

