### **Randomization of the Study Patients**

In order to assign patients to specific treatment groups in an unbiased manner, randomization will occur prior to surgery. After the patient has met the entrance criteria, and given full informed consent to participate in the study, they will be assigned to the treatment group. The randomization will be stratified by variables with potential confounding effects on the outcomes of interest. Specifically, patients will be stratified by gender (male / female), Body Mass Index category (<25.0 / 25.0-29.9 / ≥30) and age group (21-55 / 56-85). Within each stratum, subjects will be assigned to one of the two treatment groups using a computerized dynamic allocation program. Patient randomization will be performed just prior to surgery.

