### **Study Procedures**

Data Collection (obtained via a blinded research assistant)

Visit #1 Preoperative: Consent and initial data acquisition: Knee Society Clinical Rating Score, SF-12, Radiographs of the knee (standing alignment, lateral and Merchant view at 45° of knee flexion)

Visit #2 Three months: Radiographs of the knee (standing alignment, lateral and Merchant view at 45° of knee flexion); Knee Society Clinical Rating Score, SF-12. These questionnaires can be obtained in-office, by phone or by mail. While it is preferred that the visit occur in the clinic, if the participant is not returning they will still be asked to complete the study questionnaires.

Visit #3

Two years: As above #2. These questionnaires can be obtained inoffice, by phone or by mail. While it is preferred that the visit occur in the clinic, if the participant is not returning they will still be asked to complete the study questionnaires.

Visit #4

Five years: As above. These questionnaires can be obtained in-office, by phone or by mail. While it is preferred that the visit occur in the clinic, if the participant is not returning they will still be asked to complete the study questionnaires.

Visit #5

Seven years: As above. These questionnaires can be obtained in-office, by phone or by mail. While it is preferred that the visit occur in the clinic, if the participant is not returning they will still be asked to complete the study questionnaires.

Visit #7

Ten years: As above. These questionnaires can be obtained in-office, by phone or by mail. While it is preferred that the visit occur in the clinic, if the participant is not returning they will still be asked to complete the study questionnaires.

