**Secondary Efficacy Hypothesis** 

For the secondary efficacy parameters (when data is available), a non-inferiority

hypothesis will be tested at each scheduled follow-up visit, similar to the primary efficacy

hypothesis.

In addition, a comparison of the scores at each post-surgery visit with baseline (i.e.,

improvement scores) will be tested to see if any improvement is seen for each parameter

and time point.

For categorical secondary parameters (i.e., radiographic success/failure, subsidence and

radiolucency), the non-inferiority alternative hypothesis is that the risk in the X3

polyethylene group is not  $\Delta_0$ % worse relative to the N2Vac treated group within the

period from surgery to the scheduled follow-up visit. Formally the non-inferiority null

and alternative hypotheses are:

 $H_{NI,O}$ :  $\pi_{X3}/\pi_{N2Vac} > \Delta_0$ , and

 $H_{NI,A}$ :  $\pi_{X3}/\pi_{N2Vac} < \Delta_0$ , where  $\pi_{X3}$  is the rate in the Triathlon CR Total Knee

System group using the X3 polyethylene,  $\pi_{N2Vac}$  is the rate in the Triathlon CR

Total Knee System group using the N2Vac, and  $\Delta_0$  is the equivalence limit

difference ( $\Delta_0$ ).

For continuous secondary parameters (i.e., ROM, KSS, SF12), the non-inferiority

alternative hypothesis is that the mean using the X3 polyethylene is not  $\Delta_0$  worse than the

mean using the N2Vac treated group within ten years. Formally the non-inferiority null

and alternative hypotheses are:

 $H_{NI,O}$ :  $\mu_{X3} \ge \mu_{N2Vac} + \Delta_0$ , and

 $H_{NI,A}$ :  $\mu_{X3} < \mu_{N2Vac} + \Delta_0$ , where  $\mu_{X3}$  is the mean in the Triathlon CR Total Knee System group using the X3 polyethylene,  $\mu_{N2Vac}$  is the mean in the Triathlon CR Total Knee System group using the N2Vac, and  $\Delta_0$  is the equivalence limit difference ( $\Delta_0$ )..

The equivalence limit differences are as follows.:

Parameter	Equivalence Limit Difference ( $\Delta_0$ )
Range of Motion (ROM)	10 degrees
KSS pain and motion	10%
SF-12	10%
Radiographic success/failure	No complete radiolucent lines
Subsidence and Radiolucency	No component subsidence

In addition, for the continuous parameters, a comparison of the scores at each postsurgery visit with baseline (i.e., improvement scores) will be tested to see if any improvement is seen for each parameter at each time point. That is, the formal hypothesis to be tested is that the difference is zero. This is tested by:

$$H_{I,O}$$

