# **Missing Data**

Scores for missing SF-12 data will be imputed using the SF Health Outcomes Scoring Software. Both raw and imputed results will be reported. The imputed values will be analyzed.

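### Minor, nearly free improvement: the between-group intervals for ROM, KSS and SF-12 adjust for neither baseline nor the randomisation strata, so they are valid but wider than they need be

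*Combined protocol and SAP*

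**What the plan says.** - **Between-group interval.** Efficacy Analyses, Methods, on the continuous secondary parameters at each visit: "The 95% confidence interval on the difference between the two groups will be computed using the means, t-distribution and appropriate standard deviation". No covariate is mentioned.
- **Change scores.** Data Summary promises that the "improvement from baseline at each post-baseline visit for each treatment group and their difference will be presented with its 95% confidence intervals". This uses baseline by subtraction, not as a covariate.
- **Regression.** The Summary says: "Other outcome measures incorporated in the Knee Society Clinical rating scale will undergo appropriate generalized linear regression for the type of outcome involved". It covers Knee Society outcomes only and names no covariates, and the methods section does not take it up.
- **Hypothesis.** Secondary Efficacy Hypothesis covers ROM, KSS and SF-12. The non-inferiority "alternative hypothesis is that the mean using the X3 polyethylene is not" worse than the N2Vac mean by Δ0. Δ0 is 10 degrees for ROM and 10% for KSS and SF-12. The section says testing is similar to the primary.
- **Decision rule.** Only the primary parameter has one in words: "Otherwise, if the upper end of the confidence interval is less than 1.2, then the non-inferiority hypothesis will be supported".
- **Data available for adjustment.** Randomization of the Study Patients says: "The randomization will be stratified by variables with potential confounding effects on the outcomes of interest", namely sex, three BMI classes and two age groups. The preoperative visit covers "Consent and initial data acquisition: Knee Society Clinical Rating Score, SF-12, Radiographs of the knee". Baseline ROM is not listed there by name.
- **Missing values.** "Scores for missing SF-12 data will be imputed using the SF Health Outcomes Scoring Software". Nothing equivalent is given for KSS or ROM.

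**The concern.** The trial stratifies on factors that the plan itself regards as related to outcome, and it collects KSS and SF-12 before surgery. A comparison of raw follow-up means uses neither, and a comparison of change scores uses baseline inefficiently. ANCOVA on the same data gives an interval that, apart from a few degrees of freedom, is never wider than either.

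What is at stake is precision on secondary outcomes, not validity. There is also a drafting gap. Knee Society outcomes have two unreconciled descriptions of their analysis, and no sentence says which interval, or which limit of it, decides non-inferiority.

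**Working it through.** **Inputs from the plan.** 260 per group before loss (Sample Size Justification), two-sided 0.05, ROM margin 10 degrees. The plan gives no design figure for ROM, KSS or SF-12. Its only one is for revisions, and it reproduces: 26/0.05 = 520, or 260 per group, and 520 × 1.10 = 572. A standard log-rank event formula for a ratio of 0.32 at 80% power gives 25 events, close to the stated 26.

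**Assumed, because not in the documents.** The correlation r between baseline and follow-up, equal SDs at the two times, the share of variance explained by the strata, and a ROM SD of 10 to 20 degrees.

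**Step 1: width relative to the raw-means interval.** Raw = 1. Change score = sqrt(2(1 − r)). ANCOVA on baseline = sqrt(1 − r²).

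| r | Change score | ANCOVA | ANCOVA narrower than raw by | Narrower than the better planned interval by |
|---|---|---|---|---|
| 0.1 | 1.342 | 0.995 | 0.5% | 0.5% |
| 0.2 | 1.265 | 0.980 | 2% | 2% |
| 0.3 | 1.183 | 0.954 | 5% | 5% |
| 0.5 | 1.000 | 0.866 | 13% | 13% |
| 0.6 | 0.894 | 0.800 | 20% | 11% (1 − 0.800/0.894) |

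Below r = 0.5 the raw interval is the better planned one. Above it, the change score is. The two tie at r = 0.5, where the gain over the better one peaks.

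**Step 2: the same in patients.** Against the raw interval, 260 adjusted per arm has the precision of 260/(1 − r²) unadjusted: 286 at r = 0.3, 347 at r = 0.5, 406 at r = 0.6. Against the change score at r = 0.6, the variance ratio is 0.80/0.64 = 1.25, so the equivalent is 260 × 1.25 = 325.

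**Step 3: strata alone.** If they explain 2%, 5% or 10% of variance, the relative width is sqrt(1 − R²) = 0.990, 0.975 or 0.949. Because allocation is balanced on them, the unadjusted interval is slightly conservative: its one-sided error is 0.0239, 0.0222 or 0.0194 against a nominal 0.025. In a simulation with 12 balanced, prognostic strata and N = 520 (4,000 runs), the unadjusted interval covered 96.4% and the adjusted one 94.9%.

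**Step 4: the ROM verdict.** The raw half-width is t(0.975, 518) × SD × sqrt(2/260) = 0.1723 × SD. That is 1.72, 2.58 and 3.45 degrees at SD 10, 15 and 20. With ANCOVA at r = 0.3 it becomes 1.64, 2.47 and 3.29. With no true difference and a 10-degree margin, power is already 0.9999 at SD 20 and higher at the smaller SDs.

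**Step 5: KSS and SF-12.** The same calculation cannot be done. No SD is given, and the 10% margin has no stated base.

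**Step 6: direction.** The printed alternative is μ_X3 < μ_N2Vac + Δ0. Where higher is better, a much worse X3 mean would satisfy it. The intended condition for such outcomes is μ_X3 − μ_N2Vac > −Δ0.

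**The case against.** The strongest reply is that nothing is shown to go wrong. The intervals are valid, the ROM conclusion would not move, and no effect on KSS or SF-12 can be shown. That stands, and it is why the point is minor.

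Four stronger readings are tempting, and the documents do not support them:

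- *Baseline information is thrown away, and up to 20% of the width can be recovered.* Data Summary already plans an interval on the difference in improvement, and against it the gain at r = 0.6 is about 11%. The plan does not, however, name that interval as the decider.
- *A gain of at least 5% is assured.* No r is given. Follow-up runs to ten years, and nothing sets 0.3 as a floor. At r = 0.1 the gain is 0.5%.
- *KSS will be analysed without covariates.* The Summary's regression leaves covariates unnamed, which is not the same as excluding them. For KSS the fault is two descriptions that are not reconciled.
- *There is no decision rule for these outcomes.* The hypothesis section ties them to the primary, whose confidence-limit rule is explicit. The rule is implied and needs only to be written out.

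It is also fair to say that missing baselines may be rare, since baseline is taken before randomisation. The plan gives no rate, and its 10% loss figure concerns follow-up. The population section's wish to use all subjects with any data is itself qualified by feasibility.

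**Conclusion.** The point holds as a minor, nearly costless improvement. The planned intervals for ROM, KSS and SF-12 are valid as regards adjustment, taking observations as independent, but wider than necessary. The gain from ANCOVA on baseline is about 0% to 13% in width against the better of the two planned intervals, and 0.5% to 20% against the raw interval for r from 0.1 to 0.6. Both ranges rest on assumed correlations and equal SDs. If r is near zero there is almost no gain from baseline, and almost no cost. The strata would add little: 1% to 5% on their own if they explain 2% to 10% of variance.

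No conclusion is shown to change. ROM non-inferiority with no true difference has power above 99.9% either way. The effect on the KSS and SF-12 verdicts cannot be computed from the documents. The reversed inequality and the undefined 10% are separate defects in the same text. Until they are settled, no interval, adjusted or not, can decide those outcomes.

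**What to change.** In Efficacy Analyses, Methods (Secondary Parameters):

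1. Make the between-group analysis at each visit an ANCOVA of the follow-up value on randomised group, baseline value, sex, BMI class and age group. State that this is the regression meant in the Summary. Keep raw means and change scores as supportive.
2. Apply the primary's confidence-limit rule to these outcomes in words. Where higher is better, the lower 95% limit of X3 minus N2Vac must exceed −Δ0. Correct the inequality in Secondary Efficacy Hypothesis to match, and set the direction for extension according to how it is recorded.
3. State what the 10% for KSS and SF-12 is a percentage of.
4. Keep any subject with a missing baseline in the model, for example by imputing the overall baseline mean regardless of group. As an illustration only, with r = 0.3 and an assumed 10% of baselines missing at random, dropping those subjects makes the interval 0.7% wider than raw. Imputing keeps it 4.0% narrower.
5. Confirm that baseline ROM is recorded.

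The cost is SAP wording and a few lines of SAS, with no extra patients or visits. Baseline KSS, SF-12 and the strata are already collected. The change must be fixed before treatment-group data are examined.
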